- Filgotinib 200 mg monotherapy group: Filgotinib (200 mg q.d.) + PTM filgotinib 100 mg (PTM q.d.) + PTM MTX (PTM once weekly) (N=200)
- MTX monotherapy group: PTM filgotinib 100 mg (PTM q.d.) + PTM filgotinib 200 mg (PTM q.d.) + MTX (once weekly up to 20 mg) (N=400)

Randomization will be stratified by geographic region and presence of rheumatoid factor (RF) or anti-CCP (cyclic citrullinated peptide) antibody (Ab) at Screening.

[figure not shown]
At Week 24, subjects who have not achieved at least a 20% improvement from Day 1 in both swollen joint count (SJC) and tender joint count (TJC) will discontinue investigational study drug dosing but will continue with study visits and assessments per protocol. All subjects meeting this criterion who discontinue from investigational therapy are to receive standard of care treatment for their RA as determined by the investigator. Subjects achieving at least a 20% improvement in SJC and TJC at Week 24 will continue on the dosing regimens to which they were randomized through Week 52.

All subjects who continue on study drug will be evaluated for loss of therapeutic response from Week 30 through Week 52. Subjects failing to maintain at least a 20% improvement from Day 1 in TJC and SJC, (which is confirmed at 2 consecutive visits), will discontinue from investigational study drug dosing but will continue with study visits and assessments per protocol. All subjects meeting this criterion who discontinue from investigational study drug dosing are to receive standard of care treatment for their RA as determined by the investigator.

All subjects who have received at least one dose of study drug and exit the study early will complete an early termination (ET) visit at the time of study discontinuation, with a post treatment visit four weeks after the last dose of study drug (Post Treatment Week 4) regardless of dosing duration.

At completion of the 52-week study period, subjects who have not discontinued assigned study drug dosing, will be provided the option to enroll into a separate Long Term Extension (LTE) study (GS-US-417-0304).

Study Design

Number of Subjects Planned:

Approximately 1200 subjects

Target Population:

Male or female subjects who are ≥18 years of age with a diagnosis of RA meeting the 2010 ACR/ European League Against Rheumatism (EULAR) criteria, who have active RA and had limited or no prior exposure to MTX.

Duration of Treatment:

Up to 52 weeks

Diagnosis and Main Eligibility Criteria:

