For a complete list of study inclusion and exclusion criteria, please refer to Sections 4.2 and 4.3.

Main Eligibility Criteria

- 1) Male or female subjects who are ≥18 years of age, on the day of signing informed consent
- 2) Have a diagnosis of RA (2010 ACR/ EULAR criteria), and are ACR functional class I-III
- 3) Have ≥6 swollen joints (from a SJC66) and ≥6 tender joints (from a TJC68) at Screening and Day 1

- 4) Must meet at least one of the following parameters at Screening:
 - positivity for either RF or anti-CCP Ab per central laboratory
 - OR
 - Serum CRP \geq 4 mg/L based on central laboratory value
 - OR
 - \geq 1 documented joint erosion on radiographs of the hands, wrists or feet by central reading
- 5) Limited or no prior treatment with MTX, ie, no more than 3 doses of MTX \leq 25 mg each in their lifetime for the treatment of RA, with last dose at least 28 days prior to Day 1, and are an appropriate candidate for MTX therapy, as per investigator judgment

Study Procedures/
Frequency:

The subjects will visit the clinical study center at Screening, Day 1, Weeks 2, 4, 8, 12, 16, 20, 24, 30, 36, 44, and 52 or ET.

For those subjects not entering the LTE, a follow-up visit will be planned 4 weeks after the last dose of study drug (Post Treatment Week 4). Consequently, subjects are planned to be in the study for approximately 60 weeks.

During the Screening period, the subject's radiographs (hands, wrists, and feet) will be sent for blinded central scoring. In addition, information on demographics, medical history/concomitant diseases, prior and current RA medications will be collected. A physical examination, a 12-lead electrocardiogram (ECG), and clinical laboratory assessments will be conducted to determine the subject's eligibility for study participation. The screening window may be extended to up to 42 days prior to the Day 1 visit for subjects who require repeat collection of radiographs only.

At Day 1, after the subject's eligibility for the study has been confirmed, the subject will be randomized to receive one of 4 dosing regimens: filgotinib 200 mg q.d. plus MTX up to 20 mg weekly, filgotinib 100 mg q.d. plus MTX up to 20 mg weekly, filgotinib monotherapy 200 mg q.d. or MTX monotherapy up to 20 mg weekly.

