1.3. Rationale for This Study

Over the last decade, changes in RA treatment strategies, accompanied by advances in drug development and the addition of targeted biological therapies, have greatly improved the outcomes for subjects with RA. Despite these developments, therapeutic challenges remain. The current conventional and biologic DMARDs may be ineffective or produce only partial responses in some subjects and may be associated with significant safety and tolerability concerns. There is a medical need for simple, orally administered therapies with novel and targeted mechanisms of action that can effectively improve the disease course while being safe and well-tolerated. MTX-naïve patients with RA have several medications to choose from, however, it is clear that as patients progress through the available therapies, they may be left with active disease and a need for additional options. Development of another drug for these patients is appropriate, since participation in this study will not preclude the use of approved RA therapies for these subjects in the future. Moreover, all subjects in this study will receive active drug: MTX, filgotinib, or a combination of the two, as well as frequent monitoring of their health and RA status. Any subjects considered to be non-responders at Week 24 and those with loss of response at 2 consecutive visits after week 30, will discontinue study drug and take standard of care medications.

Filgotinib is an orally administered, small molecule inhibitor of JAK1, an intracellular tyrosine kinase that is dysregulated in subjects with inflammatory disorders, including RA. Filgotinib has demonstrated clinical activity and a favorable safety and tolerability profile in Phase 2 studies in subjects with moderately to severely active RA.

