1.3.1. Rationale for Study Design

The current study (GS-US-417-0303) is a Phase 3, randomized, double-blind, placebo and active-controlled study designed to evaluate the efficacy and safety of filgotinib in subjects with active RA who have limited or no prior exposure to MTX therapy. Study drugs will be administered for up to 52 weeks. The objectives of the study are to evaluate the efficacy of filgotinib as monotherapy, and in combination with MTX on the signs and symptoms of RA, to evaluate effects on physical function and radiographic progression, and to assess work productivity, fatigue, and quality of life. In addition, the safety, tolerability and pharmacokinetics (PK) of filgotinib will be assessed.

The active comparator in this study is oral MTX. Methotrexate is the most commonly prescribed first line csDMARD in the treatment of moderately to severely active RA and has been shown to reduce the signs and symptoms of disease as well as to inhibit radiographic progression {Lopez-Olivo et al 2014}. The inclusion of MTX will allow comparison of the efficacy and safety of filgotinib to an approved and frequently prescribed product indicated for use in treatment-naïve patients {Lopez-Olivo et al 2014}. In this study, MTX will be titrated up to the maximal tolerated dose over a period of 8 weeks. Non-responders at Week 24 (as defined in Section 3.2) will discontinue investigational therapy but will continue with study visits and assessments per protocol. All subjects who discontinue from investigational therapy will receive standard of care treatment for their RA as determined by the investigator.

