Given that all subjects will receive at least one active drug in this study, determining non-responder status at 24 weeks is considered both clinically and ethically appropriate and allows an acceptable time to assess initial response to therapy, especially since MTX will be titrated upward over an 8 week period. The study eligibility criteria are consistent with those of recent clinical trials evaluating novel investigational treatments for RA. Subjects should meet the 2010 ACR/European League Against Rheumatism (EULAR) criteria for RA, and are required to have active disease, defined as ≥ 6 swollen and ≥ 6 tender joints at both Screening and Day 1, as well as one of the following: the presence of at least 1 joint erosion on radiographs of the hands, wrists, or feet, or a positive test for anti-citrullinated peptide antibody (anti-CCP Ab) or rheumatoid factor (RF), or an elevated CRP level. The study duration of up to 52 weeks allows sufficient time to evaluate safety, reduction in disease activity, and confirmation that clinical benefit is sustained over time.

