3.2. Study Design

This is a randomized, double-blind, placebo- and active-controlled, Phase 3 study in adult male and female subjects with moderately to severely active RA who have limited or no prior exposure to MTX therapy. The study is designed to evaluate the efficacy, safety and tolerability of filgotinib as well as its effect on patient-reported outcomes, including work productivity, fatigue, and quality of life. In addition, PK will be assessed.

Adult male and female subjects with active RA will be screened to determine eligibility as per the inclusion and exclusion criteria (see Section 4.2 and 4.3, respectively). The Screening period will be up to 28 days. The screening window may be extended to up to 42 days prior to the Day 1 visit for subjects who require repeat collection of radiographs.

Written informed consent must be obtained before any study-related procedures take place. During the Screening period, following signing of the informed consent form (ICF), the subject's radiographs (hands, wrists, and feet) will be sent to central review for confirmation of joint erosion (see inclusion criterion 5; Section 4.2). Note that the subject's radiographs need to be sent to central review as soon as possible after completion and prior to Day 1 to allow for central reading and confirmation of one or more joint erosion in subjects that are seronegative.

Subjects will be randomized in a 2:1:1:2 ratio to filgotinib 200 mg plus MTX, filgotinib 100 mg plus MTX, filgotinib 200 mg alone, or MTX alone for up to 52 weeks in a double-blind fashion.

At Week 24, subjects who have not achieved a 20% improvement from Day 1 in both SJC and TJC will discontinue investigational therapy but will continue with study visits and assessments per protocol. All subjects who discontinue from investigational therapy are to receive standard of care treatment for their RA as determined by the investigator.

Responders at Week 24 will continue on the treatment regimens to which they were randomized through Week 52.

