3.5. Criteria for Interruption or Discontinuation of Study Treatment

3.5.1. Study drug interruption considerations:

The Gilead Medical Monitor should be consulted prior to study drug interruption when medically feasible.

Study drug interruption should be considered in the following circumstances; *prior to resumption of study drug, the investigator should discuss the case with the Gilead medical monitor:*

- Intercurrent illness that would, in the judgment of the investigator, affect assessments of clinical status to a significant degree.
- Subject is scheduled for elective or emergency surgery (excluding minor skin procedures under local or no anesthesia); timing of study drug pausing should be determined in consultation with the Gilead medical monitor.
- Any subject who develops a new infection during the study should undergo prompt and complete diagnostic testing appropriate for an immunocompromised individual, and the subject should be closely monitored.

NOTE: During the time of study drug interruption for any of the above, the subject may continue to have study visits and to take part in procedures and assessments, if deemed medically appropriate by the investigator.

3.5.2. Study drug discontinuation considerations:

The Gilead Medical Monitor should be consulted prior to study drug discontinuation when medically feasible.

Study medication should be permanently discontinued in the following instances:

- Any opportunistic infection
- Any **serious** infection that requires antimicrobial therapy or hospitalization, or any infection that meets SAE reporting criteria.
- Complicated herpes zoster infection (with multi-dermatomal, disseminated, ophthalmic, or CNS involvement)
- Evidence of active HCV during the study, as evidenced by HCV RNA positivity
- Evidence of active HBV during the study, as evidenced by HBV DNA positivity
- Unacceptable toxicity, or toxicity that, in the judgment of the investigator, compromises the subject's ability to continue study-specific procedures or is considered to not be in the subject's best interest
- Non-responder at Week 14 OR at 2 consecutive visits after Week 30 as outlined in Section 3.2
- Subject request to discontinue for any reason
- Subject noncompliance
- Pregnancy during the study (Section 7.7.2.1 and Appendix 5)
- Discontinuation of the study at the request of Gilead, a regulatory agency or an institutional review board or independent ethics committee (IRB/IEC)

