5.3.4. Dosage and Administration of MTX

The titration period for MTX will be 8 weeks. Subjects will be started on 10 mg (4 capsules) of either MTX or PTM, in a blinded fashion. In the absence of any lack of tolerance as specified below, subjects will be advanced to 15 mg (6 capsules) of MTX or PTM at their 4 week visit and advanced to 20 mg (8 capsules) of MTX or PTM at their 8 week visit. Subjects should be on an adequate dose of folic acid (as per local practice) which should be confirmed or initiated at Day 1, and continued throughout the study.

All local standard-of-care practices for the administration of MTX, including follow-up care and contraindications should be performed according to local standards of care throughout the study.

Events that might indicate a lack of tolerance *may include, but are not limited to:*

- Moderate to severe headaches not responding to simple medical management;
- Moderate to severe nausea not responding to simple medical management;
- Moderate to severe fatigue;
- Mucocutaneous problems: oral ulcers or stomatitis not responding to simple medical management;
- Alopecia not responding to simple medical management;
- Elevated transaminases, confirmed by two consecutive blood tests (3-7 days apart);
- Cytopenia, on blood samples taken 3-7 days apart:
 - Thrombocytopenia, defined as two sequential platelet counts <100,000 platelets/mm³;
 - Neutropenia, defined as two sequential neutrophil counts <1.0 x 10⁹/L;
 - Leukopenia, defined as two sequential white blood cell count <3.0 x 10⁹/L;

Simple medical management of adverse events typical of suspected intolerance to MTX may include allowed concomitant medications (e.g., anti-emetic medication), or replacing folic acid with up to 5 mg dose of leucovorin (folic acid) dosed 8 to 24 hours after the MTX weekly dose.

Single Dose Reduction of Methotrexate

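### Protocol Section 3.5.2 sets the non-responder stop at Week 14, but Section 3.2, which it cites, sets it at Week 24, and there is no Week 14 visit

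*Protocol*

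**What the plan says.** Section 3.5.2 of the protocol gives the circumstances in which study medication should be permanently discontinued. One bullet reads "Non-responder at Week 14 OR at 2 consecutive visits after Week 30 as outlined in Section 3.2".

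Section 3.2, to which the bullet points, says: "At Week 24, subjects who have not achieved a 20% improvement from Day 1 in both SJC and TJC will discontinue investigational therapy". It adds a separate check for loss of response from Week 30 to Week 52, confirmed at two consecutive visits.

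Section 1.3 refers to "Any subjects considered to be non-responders at Week 24 and those with loss of response at 2 consecutive visits after week 30". Section 1.3.1 says "Non-responders at Week 24 (as defined in Section 3.2) will discontinue investigational therapy" and defends the timing: "determining non-responder status at 24 weeks is considered both clinically and ethically appropriate". The synopsis and SAP Section 1.2 also state the rule at Week 24. SAP Section 6.1 ties its exclusion of later efficacy data to the nominal Week 24 visit, with Week 30 as the fallback when Week 24 status cannot be determined.

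The synopsis lists post-baseline visits at "Weeks 2, 4, 8, 12, 16, 20, 24, 30, 36, 44, and 52 or ET".

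**The concern.** The bullet gives a decision time that differs from the section it cites and from every other dated statement of the rule. It appears in the list a site would consult when deciding whether to end treatment, alongside the infection, hepatitis and laboratory stops.

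Week 14 also undercuts the stated reason for waiting. Section 1.3.1 supports a 24-week assessment partly because MTX is titrated over 8 weeks, and Section 5.3.4 has subjects "advanced to 20 mg (8 capsules) of MTX or PTM at their 8 week visit".

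A subject stopped early on a literal reading would lose up to 10 weeks of randomized treatment before the intended decision point. Under Section 3.7 that subject would be ineligible for the extension study. The subject would also have no on-treatment data in the Week 24 window for ACR20, DAS28(CRP) and HAQ-DI.

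**Working it through.** **Statements of the stop, side by side**

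| Place | Time of non-responder stop |
|---|---|
| Protocol 3.5.2 | Week 14 |
| Protocol 3.2 (cited by 3.5.2) | Week 24 |
| Protocol synopsis, Study Design | Week 24 |
| Protocol 1.3 | Week 24 |
| Protocol 1.3.1 (also cites 3.2) | Week 24 |
| SAP 1.2 and 6.1 | Week 24 |

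Footnote v of the study procedures table (Appendix 2), which carries this stop, does not mention Week 14. Week 14 appears nowhere else in either document.

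**Position in the schedule.** Study Day = 7 × week + 1, which reproduces SAP Table 3-1 (Week 12 = 85, Week 16 = 113, Week 24 = 169). Week 14 is therefore 7 × 14 + 1 = Day 99. With the ±3-day windows of Appendix 2, the Week 12 visit covers Days 82–88 and the Week 16 visit Days 110–116. Day 99 falls in neither, so no joint count is scheduled then.

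**Time at full MTX dose.** The 20 mg step is at Week 8. Week 14 allows 14 − 8 = 6 weeks at that dose; Week 24 allows 24 − 8 = 16 weeks.

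**Loss of the Week 24 value.** SAP Section 3.8.2 ends the on-treatment period 7 days after the last dose, and Table 3-1 opens the Week 24 window on Day 156. The last dose is taken to be on the decision day.

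| Stop at | Last dose (day) | On-treatment data end (day) | Gap to Day 156 |
|---|---|---|---|
| Week 12 visit | 85 | 92 | 64 days |
| Week 14, literal | 99 | 106 | 50 days |
| Week 16 visit | 113 | 120 | 36 days |

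In each case the subject has no on-treatment value in the Week 24 window. The primary efficacy dataset is on-treatment (SAP 6.1), so non-responder imputation (SAP 6.2.3 and 6.3.2) scores the subject as a failure on ACR20 and DAS28(CRP) < 2.6.

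**Who is affected.** ACR20 requires at least 20% improvement in both joint counts (SAP 6.2.1). A subject stopped under the joint-count rule is not an ACR20 responder at that moment. The ACR20 result changes only for those who would have responded by Week 24.

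**Effect per subject.** 1/400 = 0.25 percentage points in a 400-subject arm; 1/200 = 0.5 in a 200-subject arm.

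**Illustrative bound on power.** Two-proportion test, pooled variance under the null, two-sided 0.05, with the planned 78% on filgotinib against 62% in 400 MTX subjects. All losses are assumed to fall in the filgotinib arm, which is the worst case.

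| Filgotinib arm | Would-be responders lost | Rate | Power |
|---|---|---|---|
| n = 400 | 0 | 78.0% | 0.9988 |
| n = 400 | 21 | 72.75% | 0.9017 |
| n = 400 | 22 | 72.5% | 0.8872 |
| n = 200 | 0 | 78.0% | 0.9827 |
| n = 200 | 5 | 75.5% | 0.9208 |
| n = 200 | 6 | 75.0% | 0.8987 |

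If the same fraction is lost in both arms, power barely moves: 0.9975 with 22 lost from each 400-subject arm, and 0.977 with 6 of 200 and 12 of 400 lost.

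**The case against.** The strongest reply is that the documents resolve the slip themselves. The bullet sets no criterion of its own; it defers to Section 3.2, which gives both definition and time. The rule cannot be applied at a scheduled Week 14 visit because none exists. The section heading speaks of considerations, the verb is should, and the medical monitor is to be consulted first. All of this stands, and it is why the point is minor. The safeguards are incomplete, though: consultation applies only when medically feasible, and the conflict is visible only to a reader who follows the cross-reference.

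The 50-day gap assumes a stop on a day with no planned joint count, so a site would more likely act at Week 12 or Week 16, or call an unscheduled visit. That is fair, but the gap at either scheduled visit (64 or 36 days) leads to the same result.

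Putting all losses in one arm is unrealistic in a double-blind trial, where a misreading site would treat all arms alike. This is also right. The thresholds of 22 and 6 are a worst-case bound, not a forecast.

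The remedy also has limits. Section 9.2.1 requires ethics approval of protocol modifications before they are implemented, and the synopsis plans about 200–250 centers. The discontinuation listing in SAP Section 4.1 is not stated to show dates or a non-response category, and subjects may stop early for other reasons. An early stop would therefore not by itself show that Week 14 had been applied.

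**Conclusion.** The concern holds. Section 3.5.2 states the wrong week for the non-responder stop, and Week 24 is almost certainly intended. It is a wrong number in a treatment-stopping rule and does not call into question the choice of Week 24 or the SAP's handling of early stoppers, whose general rules already cover the case.

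Severity is minor. Sample size, planned power and planned analyses do not change. The number of subjects affected cannot be known from the documents, and nothing suggests it is above zero. Even if all losses fell in the filgotinib arm, 400 versus 400 would keep power at or above 90% with up to 21 would-be responders wrongly stopped, and 200 versus 400 with up to 5. An isolated misreading would not be expected to alter the primary conclusion. These figures rest on the planned 78% and 62% response rates and full planned enrollment.

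**What to change.** In Protocol Section 3.5.2, replace Week 14 with Week 24 and tell sites of the correction. The sensible vehicle is the next protocol amendment, since modifications need ethics approval before use; a stand-alone amendment for one numeral is hard to justify.

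Use the by-subject listing of discontinuation reasons already planned in SAP Section 4.1, read with last dose dates, to look for stops for non-response before Week 24. Any such case should be queried with the site rather than assumed to be a misapplied rule.

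The cost is one numeral, its share of an amendment already going through approval, and a site notice. No extra subjects, procedures or analyses are needed.

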- Subject use of prohibited concurrent therapy *may* trigger study drug discontinuation; consultation should be made with the Gilead medical monitor.
- Laboratory criteria:

After becoming aware of any of the below described abnormal laboratory changes occurring at any one time, an unscheduled visit (ie sequential visit) should occur to retest within 3 to 7 days (except creatinine, which should be retested 7-14 days apart).

— 2 sequential neutrophil counts <750 neutrophils/mm³ (SI: $<0.75 \times 10^9$ cells/L) after dose adjustment of MTX/PTM (Section 5.3.4)

- 2 sequential platelet counts $<75,000$ platelets/mm³ (SI: $<75.0 \times 10^9$ cells/L) after dose adjustment of MTX/PTM (Section 5.3.4)
- 2 sequential AST or ALT elevations $>3 \times \text{ULN}$ and ≥ 1 total bilirubin value $>2 \times \text{ULN}$ or accompanied by symptoms consistent with hepatic injury¹ after dose adjustment of MTX/PTM (Section 5.3.4)
- 2 sequential AST or ALT elevations $>5 \times \text{ULN}$ after dose adjustment of MTX/PTM (Section 5.3.4)
- 2 sequential values for estimated creatinine clearance <35 mL/min based on the Cockcroft Gault formula

Subjects who permanently discontinue study medication for any reason are to receive standard of care treatment for their RA as determined by the investigator, and those subjects should be encouraged to continue study visits and procedures, if deemed medically appropriate by the investigator. Subjects who permanently discontinue study medication for pregnancy should not continue in the study; if there are any questions regarding permanent discontinuation, these should be discussed with the Sponsor.

Subjects withdrawing from the study should complete ET and Post Treatment Week 4 visits. Subjects are free to withdraw from the study at any time without providing reason(s) for withdrawal and without prejudice to further treatment. The reason(s) for withdrawal will be documented in the electronic case report form (eCRF).

Reasonable efforts will be made to contact subjects who are lost to follow-up. These must be documented in the subject's file.

The sponsor has the right to terminate the study at any time in case of safety concerns or if special circumstances concerning the study medication or the company itself occur, making further treatment of subjects impossible. In this event, the investigator(s) and relevant authorities will be informed of the reason for study termination.

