After the first 4 weeks, a single dose reduction of MTX/PTM by 5 mg (2 capsules weekly) is allowed during the study, as long the patient remains on a dose of at least 4 capsules of MTX/PTM weekly. Lack of tolerance and dose reductions are to be documented by the investigator. Should significant laboratory abnormalities or symptoms persist after dose adjustment, please refer to the discontinuation guidelines as outlined in Section 3.5. If the subject cannot tolerate the MTX/PTM tablets within the first 4 weeks of the study, consideration should be given to discontinuing the subject from study drug dosing, as no dose reduction is permitted within the first 4 weeks.

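### Four of the five laboratory stopping rules in Protocol 3.5.2 depend on an MTX dose adjustment that 5.3.4 does not offer in the first 4 weeks

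*Protocol*

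**What the plan says.** Protocol 3.5.2 gives five laboratory criteria for permanent discontinuation, each confirmed by a retest (3 to 7 days later, or 7 to 14 days for creatinine). Neutrophils below 750/mm³, platelets below 75,000/mm³, AST/ALT above 3 x ULN with bilirubin above 2 x ULN or hepatic symptoms, and AST/ALT above 5 x ULN all apply "after dose adjustment of MTX/PTM (Section 5.3.4". Creatinine clearance below 35 mL/min carries no such condition.

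Section 5.3.4 starts every subject on 4 capsules (10 mg). The next step is at the Week 4 visit: "In the absence of any lack of tolerance as specified below, subjects will be advanced to 15 mg (6 capsules) of MTX or PTM". After the first 4 weeks one reduction of 2 capsules is allowed, "as long the patient remains on a dose of at least 4 capsules of MTX/PTM weekly". For intolerance before then the text is: "consideration should be given to discontinuing the subject from study drug dosing, as no dose reduction is permitted within the first 4 weeks". The section sends the reader back to the stopping rules with "Should significant laboratory abnormalities or symptoms persist after dose adjustment, please refer to the discontinuation guidelines as outlined in Section 3.5".

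Its examples of lack of tolerance include "Elevated transaminases, confirmed by two consecutive blood tests (3-7 days apart", "Thrombocytopenia, defined as two sequential platelet counts <100,000" per mm³, and "Neutropenia, defined as two sequential neutrophil counts" below 1.0 x 10⁹/L.

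**The concern.** The two sections refer to each other without covering the first 4 weeks. Section 3.5.2 makes the stop wait for an adjustment under 5.3.4. Section 5.3.4 offers none in that window and points back to 3.5 only for abnormalities that persist after one. The evident logic is to reduce first and stop if that fails. Where reduction is unavailable, that logic leads straight to stopping, yet the text gives the weaker instruction to consider it.

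At stake is whether a confirmed result at a threshold the sponsor has already judged serious enough to end dosing has the same consequence at Week 2 as later. The window is not an arbitrary one. Protocol 1.2.3 reports that in the Phase 2b study of filgotinib with MTX, mean neutrophil and platelet counts fell in a dose-dependent way up to Week 4 and then levelled off. Section 1.4 adds that mean changes stayed within reference ranges, so threshold crossings should be rare.

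**Working it through.** The documents give no figure for this gap, so the main check sets the two sections side by side.

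**1. Which stops carry the condition (3.5.2).** Neutrophils, platelets, AST/ALT above 3 x ULN with bilirubin or symptoms, AST/ALT above 5 x ULN: 4 of 5. Creatinine clearance does not.

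**2. Adjustments available (5.3.4).**

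| Period and dose | Step up | Reduction by 2 capsules |
|---|---|---|
| First 4 weeks, 4 capsules | None before the Week 4 visit | Not permitted |
| Later, 8 capsules | – | 8 − 2 = 6, allowed |
| Later, 6 capsules | – | 6 − 2 = 4, allowed |
| Later, still on 4 capsules | Withheld for intolerance | 4 − 2 = 2, below the floor of 4 |

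In the first row there is nothing to reduce and no increase to withhold. The condition fails whether adjustment means reduction alone or also a withheld increase. In the last row the answer depends on that definition.

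**3. Can a confirmed pair fall inside the window?** Week 2 is nominal Day 15 (SAP Table 3-1), with a ±3-day window (Protocol Appendix 2): Day 12 to 18. The retest 3 to 7 days later falls on Day 12 + 3 = 15 to Day 18 + 7 = 25. The 3 to 7 days run from awareness of the result, and laboratory turnaround is not stated. The pair still completes by Day 28 with a turnaround of up to 28 − 25 = 3 days in the latest case, or 28 − (15 + 7) = 6 days from nominal Day 15. A Week 4 draw cannot complete a pair in time: earliest Day 26 + 3 = Day 29.

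**4. Size of the window.** 28 / (52 × 7) = 28/364 = 7.7% of dosing days. Scheduled post-baseline safety draws in the treatment period are Weeks 2, 4, 8, 12, 16, 20, 24, 30, 36, 44 and 52. That is 11, of which only Week 2 counts.

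**5. Distance from the screening limits (4.3, criterion 33) to the stops.**
- Neutrophils, at least 1.5 to below 0.75: 1 − 0.75/1.5 = a fall of more than 50%.
- Platelets, at least 100 to below 75: 1 − 75/100 = a fall of more than 25%.
- AST/ALT, below 1.5 x ULN to above 3 or 5 x ULN: 3/1.5 = more than 2.0-fold, 5/1.5 = more than 3.3-fold.

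**6. What else applies in the window.**
- Unacceptable toxicity (3.5.2): a stop, by investigator judgment, with no number.
- 7.5.2: withhold for a related Grade 3 event (laboratory values confirmed); unrelated events may continue.
- 7.5.3: stop for a related Grade 4 event (laboratory values confirmed).
- 7.6 and the hepatic footnote to 3.5.2: medical-monitor discussion, and work-up for the liver criteria.
- 6.7.3: decide after the retest.

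None of these uses the 3.5.2 thresholds. The protocol does not print the CTCAE laboratory grades, so I do not map the thresholds to grades.

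**7. Cost of the fix in power.** Power ≈ Φ(|p₁ − p₂| / √[p₁(1−p₁)/n₁ + p₂(1−p₂)/n₂] − 1.96). The plan claims over 90% for ACR20 of 62% against 78%. The check reproduces that claim, then applies an assumed loss of 1 percentage point.

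| MTX vs filgotinib | 400 vs 400 | 400 vs 200 |
|---|---|---|
| 62% vs 78% (planned) | 99.9% | 98.8% |
| 61% vs 77% (all arms lose 1 point) | 99.9% | 98.6% |
| 62% vs 77% (filgotinib loses 1 point) | 99.7% | 97.4% |

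**The case against.** The strongest reply is that only the number is missing early, not the stop. The unacceptable-toxicity item sits in the same 3.5.2 list, under the same instruction to discontinue permanently, and has no time or MTX condition. The Grade 3 and Grade 4 rules also apply from the first dose. The sponsor's medical monitor takes part in deciding the course of action at every center, and the retest requirement has no Week 4 exclusion. Section 5.3.4 addresses the first 4 weeks expressly, so the sponsor may have chosen judgment there, alongside local MTX practice. Section 7.5 also sends sites to uniform guidelines in Appendix 3, whose content is not readable in the available text and must not be treated as absent.

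Most of this stands, and it limits the consequence. A reader might infer that a subject with confirmed liver or blood-count toxicity at Week 2 would simply stay on drug, or that each center would decide alone. The documents support neither inference. What the reply does not do is restore the fixed threshold. The toxicity item rests on judgment, and 7.5.2 and 7.5.3 depend on grade and on relatedness.

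A second reply is that mandatory discontinuation on the first confirmed pair is harsher than the later rule, where a subject on 6 or 8 capsules gets a reduction first, and that it removes the withhold-and-rechallenge route in 7.5.2. That is a real cost and is counted under the fix.

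**Conclusion.** The point holds, at minor severity. As written, four of the five laboratory stops cannot be met in the first 4 weeks, on either reading of dose adjustment. Early stopping then rests on the unacceptable-toxicity item, the instruction in 5.3.4 to consider discontinuation, the relatedness-dependent rules in 7.5.2 and 7.5.3, and medical-monitor review.

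The number of subjects affected is unknown, because the documents give no rate. It is probably small: the window is short, MTX is at its 10 mg starting dose in the arms that receive it, and the screening limits leave a long way to move.

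A reader might also infer that the stops stay out of reach after Week 4 for anyone held at 4 capsules. The documents do not settle this. Section 5.3.4 uses the term directly after describing the reduction, which favors reading it as reduction. But withholding the Week 4 step for intolerance is itself a dosing action that the section prescribes. If that counts as an adjustment, the later gap closes.

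The conclusion assumes that 3.5.2 is applied literally and that Appendix 3 does not already set a stop for these values.

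**What to change.** Three short changes to the protocol:

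- In 3.5.2, apply the dose-adjustment condition only where 5.3.4 permits a reduction; where it permits none, the criterion is met on confirmation by the second sequential value.
- In 5.3.4, state that the instruction to consider discontinuation does not override a 3.5.2 laboratory threshold that has been met.
- Define dose adjustment, including whether a withheld up-titration counts. This settles the case of subjects held at 4 capsules.

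If Appendix 3 already sets a stop for these values, a cross-reference to it in 3.5.2 is enough.

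The cost is two or three sentences in an amendment and a note to sites, with no new visits or tests. The downside is a few more early permanent discontinuations, and those subjects lose the 7.5.2 option of withholding and rechallenging. They would generally count as Week 24 ACR20 non-responders, since the SAP's primary dataset ends 7 days after the last dose (3.8.2) and missing responses are imputed as failures (6.2.3). Under the assumed 1-point losses in the check, power stays at 97.4% or higher, above the planned 90%.
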